### ***Exploratory Aims***

Exploratory analyses will evaluate the quantity and quality of adverse events observed with NTX+MEM/NAC treatment. We will also explore the effects of NTX and NTX+MEM/NAC treatment on the reaction time outcomes of Implicity Association Task and the alcohol Approach-Avoidance Task, as well as the behavioral and self-report impulsivity measures. Exploratory analyses will also examine impulsive propensities and responses on the PIT task, as predictors of treatment response. We will also evaluate potential correlations between the behavioral effects of alcohol and impulsivity measures as well as the presence of glutamate (STEP/FYN) and opioid (OPRM1) gene polymorphisms.

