In the current proposal we would like to conduct an important extension of this work. We will test the hypothesis that by targeting both opioidergic and glutamatergic mechanisms, one may synergistically target multiple neurochemical and behavioral processes, leading to optimal reduction of alcohol drinking. This pilot trial will be conducted in FHP drinkers in whom we have observed reduction in alcohol reward with MEM and in alcohol drinking with NTX. We will test the efficacy and tolerability of the combined use of MEM and NTX. We will also test the efficacy and tolerability of the combined use of N-acetyl cysteine and NTX. N-acetylcysteine (NAC), an acetyl pro-drug of cysteine is another agent which can be used to target the glutamatergic system. NAC is believed to produce its effects by stimulating the cysteine-glutamate exchanger and thus altering synaptic glutamate levels. A significant potential advantage of NAC is better tolerability, which may make it a better glutamate-altering agent to use in combination with NTX. Finally, we will also evaluate the predictive utility of impulsive responding, implicit alcohol motivational tendencies, and variations in genes for opiate receptors and for signal transduction proteins linking dopamine and glutamate receptors upon alcohol drinking behaviors.

The following specific aims will be tested:

**Primary Aim 1:** Evaluate the effects of pretreatment with a combination of naltrexone (NTX; 50 mg) and memantine (MEM; 20 mg) or N-acetylcysteine (NAC; 2400 mg) on drinking in FHP drinkers.

*Primary Hypothesis:* Combination treatment with NTX and MEM or NAC, when compared with NTX alone, will reduce number of drinks consumed during the self-administration period.  
*Exploratory hypothesis:* Combination treatment with NTX and MEM will reduce time to first drink and increase the average time to consume each drink, during the self-administration phase.

**Primary Aim 2:** Evaluate the effects of pretreatment with a combination of naltrexone (NTX; 50 mg) and memantine (MEM; 20 mg) or NAC (2400 mg) on alcohol craving in FHP drinkers  
*Hypothesis:* Combination treatment with NTX and MEM or NAC, when compared with NTX alone, will reduce alcohol craving (Yale Craving Scale) during the self-administration period  
*Exploratory hypothesis:* Combination treatment with NTX and MEM will reduce craving in response to the alcohol cue presented just prior to the priming drink period.

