**Primary Aim 3:** Evaluate the effects of pretreatment with a combination of naltrexone (NTX; 50 mg) and memantine (MEM; 20 mg) or NAC (2400 mg) on alcohol-induced stimulation in FHP drinkers.

*Hypothesis:* Combination treatment with NTX and MEM or NAC, when compared with NTX alone, will reduce alcohol-induced stimulation (Biphasic Alcohol Effects Scale) during the self-administration period.

**Secondary Aim:** Examine the tolerability of co-administration of NTX and MEM and NTX and NAC

**Exploratory Aims:** Examine the influence of innovative predictors of treatment response, including:

- ❖ Impulsive propensity and implicit alcohol associations
- ❖ Opioidergic (OPRM1) and signal transduction proteins that moderate the function of NR2B-containing NMDA receptors (Fyn kinase, STEP) genotypes
- ❖ Pavlovian to Instrumental transfer propensity

2. **Background:** Describe the background information that led to the plan for this project. Provide references to support the expectation of obtaining useful scientific data.

Alcohol use, abuse, and dependence are a huge public health problem in the United States and worldwide. Epidemiological evidence suggests that almost 17.6 million adults in the U.S. are abusing alcohol or are alcohol dependent (Grant et al., 2004), emphasizing the importance of developing optimal interventions for the treatment of this disorder. At present, three medications have been approved by the FDA in the U.S. for the treatment of alcohol dependence: disulfiram, naltrexone, and acamprosate. However, the treatments effects for these agents range from minimal to modest, and they are minimally utilized in clinical community settings (Garbutt et al., 1999; Krishnan-Sarin et al., 2009b). Therefore, there is a significant need for other medications, or combinations of medications, that are more efficacious in reducing alcohol use.

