*Clinician-Administered Dissociative States Scale (CADSS)* (Bremner et al., 1998): A 19 item self-report questionnaire with eight observer ratings designed to assess perceptual, behavioral, and attentional changes that occur during dissociative experiences from NMDA receptor antagonists (Krystal et al., 1994).

h) Intellectual Functioning: In order to obtain an assessment of general intellectual functioning and a reference point for other cognitive assessments, we will complete the two subtest short-form of Block Design and Information from the WAIS-III (Weschler, 1997). This combination correlates at .87 with the Full Scale IQ.

i) Impulsivity and Automatic Motivational Measures: Change from occasional to compulsive drug use may be less dependent on positive reinforcement and more dependent on implicit processes that automatically evaluate the motivational significance of the alcohol cue for affect regulation. Such processes may include “fast” impulsive responses which automatically orient the individual to either approach or avoid the stimulus and “slower,” more reflective processes involving conscious deliberation and emotion regulation. We will assess using impulsive responding using measures which encompass several clinically relevant core components such as rapidity of response, degree of planning, and disregard of future consequences. Additionally, we will also measure implicit alcohol-affect associations as well as individual variations in the ability of incentive stimuli to control behavior. We will evaluate changes in impulsivity and implicit alcohol associations at baseline and then after each medication period. Pavlovian to Instrumental transfer task will be assessed at baseline only.

j) Padua Inventory (Sanavio, 1988): consists of 60 items describing common obsessional and compulsive behavior and allows investigation of the topography of such problems in normal and clinical symptoms.

k) Chronic Stress Scale (CSS) (Turner et al., 1995): This measure is used to assess a person's perception of ongoing and enduring sources of stress in their life conditions. The chronic stress scale (CSS) includes a list of 51 items about common life conditions and situations (e.g., financial issues, work, marriage and relationship, parental, family, social life). The interviewer reads each item aloud and asks the respondent to reply with not true (0), somewhat true (1), or very true (2).

*Self Reports:*

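### Genotype and implicit associations are listed as predictors of treatment response, but the analysis plan gives neither a treatment contrast as a predictor

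*Combined protocol and SAP*

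**What the plan says.** Section V.1 introduces the exploratory aims with "Examine the influence of innovative predictors of treatment response, including" and lists three sets:

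- "Impulsive propensity and implicit alcohol associations"
- "Opioidergic (OPRM1) and signal transduction proteins that moderate the function of NR2B-containing NMDA receptors (Fyn kinase, STEP) genotypes"
- Pavlovian-to-instrumental transfer (PIT) propensity.

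The narrative before the aims is looser: "we will also evaluate the predictive utility of impulsive responding, implicit alcohol motivational tendencies, and variations in genes for opiate receptors", where the thing predicted is alcohol drinking behavior, not treatment response.

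Section V.4, Exploratory Aims, gives the analyses. Treatment effects are to be explored "on the reaction time outcomes of Implicity Association Task and the alcohol Approach-Avoidance Task", so IAT and AAT are dependent variables there. Prediction of response is one sentence: "Exploratory analyses will also examine impulsive propensities and responses on the PIT task, as predictors of treatment response". Genotype appears only in the next one: "We will also evaluate potential correlations between the behavioral effects of alcohol and impulsivity measures as well as the presence of glutamate (STEP/FYN", which goes on to OPRM1.

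Two other places bear on the point. Section V.3, Alcohol-Drinking Paradigm, says the impulsivity and association task data will serve to examine medication effects and the relation to drinking. Section V.3, Assessments, item i, gives the timing: "We will evaluate changes in impulsivity and implicit alcohol associations at baseline and then after each medication period". It fixes PIT at baseline only.

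**The concern.** Prognosis and prediction of response are different questions. A genotype is prognostic if carriers drink more, or react more to alcohol, in whatever condition they are tested. It predicts response if the difference between naltrexone plus an add-on and naltrexone alone is larger or smaller in carriers. The aim asks the second question. A correlation of genotype with alcohol's behavioral effects, with no treatment term, addresses the first.

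The Power Analysis section says the pilot is to supply effect size estimates for future trials. For genotype and implicit associations, the analysis as written yields no estimate of effect modification, although the data needed are due to be collected.

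A smaller matter concerns the impulsivity and implicit measures. They are taken before drug and again on drug, and Section V.4 does not say which value serves as the predictor. A value measured on drug may already be affected by treatment.

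**Working it through.** **Aim against analysis.**

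| Predictor in the Section V.1 aim | Named as predictor of response in Section V.4? | Other stated use |
|---|---|---|
| Impulsive propensity | Yes | Treatment outcome; correlation with alcohol effects |
| PIT | Yes | None stated |
| Implicit associations (IAT, AAT) | No | Treatment outcome; relation to drinking (Section V.3) |
| OPRM1, Fyn, STEP | No | Correlation with alcohol effects |

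The mismatch therefore covers two predictor sets, genotype and implicit associations. The plan gives no figure to reproduce here. The only inputs from the documents are 30 completers (3 × 10, Power Analysis) and two-sided alpha 0.05 (Section V.4). Carrier share, SDs and effect sizes are assumptions.

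**Purely prognostic genotype.** Assume 30 people and 30% carriers (9 against 21), each person measured on two treatments, between-person SD 1, within-session SD 0.7 and no interaction.

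- SD of a person's mean over two sessions: √(1 + 0.7²/2) = √1.245 = 1.116.
- Group factor: √(1/9 + 1/21) = 0.398.
- Main effect 1 SD: 1/(1.116 × 0.398) = 2.25 standard errors. On 28 df this is about 58% power for the correlation to be significant. Simulations gave 56–59%.
- Main effect 0.5 SD: 1.12 standard errors, about 19%. Simulation gave 18%.
- Main effects 0.3 and 0.2 SD: 9% and 7% in simulation.

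In every case the genotype-by-treatment test, which compares the within-person difference between carriers and non-carriers, is significant about 5% of the time. That is its nominal rate.

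**A different variance assumption.** With total SD 1 and within-person correlation 0.5, the SD of the mean is √(0.5 + 0.25) = 0.866. A 1 SD main effect then gives 1/(0.866 × 0.398) = 2.90 standard errors, about 80%, against 5% for the interaction test.

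**Purely predictive genotype.** With the same variances, the SD of the within-person difference is √(2 × 0.5) = 1. A 1 SD interaction with no average effect across conditions gives 1/0.398 = 2.51 standard errors. The interaction test detects it in 68% of trials and the pooled correlation in 5%.

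**Precision of the interaction.** The difference detectable at 80% power is (1.96 + 0.84) × √(1/n₁ + 1/n₀), in SDs of the within-person treatment difference, for carrier shares from 50% to 20%:

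- 30 people: 1.02 to 1.28
- 20 people: 1.25 to 1.57
- 10 people: 1.77 to 2.21

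All three are shown because the documents do not say how many people contribute to each add-on contrast. With all 30, power is 19–28% for a 0.5 SD difference and 42–59% for 0.8 SD.

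**The case against.** The strongest reply is that the aim is worded in two ways. Predictive utility for drinking behavior, as the Section V.1 narrative has it, is partly served by a correlation. That stands, but the formal aim says treatment response, and Section V.4 uses the same phrase for two predictors and not for the others.

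A second reply is that impulsive propensities could be read to include the implicit tasks, since Section V.1 puts them in one bullet and Section V.3 discusses them under one heading. This is possible. However, Section V.4 lists IAT and AAT apart from the impulsivity measures one sentence earlier, so the reading is not secure, and it does nothing for genotype.

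Third, a correlation with the within-person difference between treatments would show prediction of response. True, but the plan does not say that this is the quantity correlated.

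Four stronger readings are tempting and not supported:

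- That the investigators will call a correlated genotype a predictor of response. Section V.4 keeps prediction and correlation in separate sentences and never says this.
- That the implicit tasks are used only as outcomes throughout. Section V.3 also relates them to drinking.
- That on-drug values will be used as predictors. The plan is silent on which value is used, and baseline values are collected.
- That the correlation misleads in most trials. The 56–59% needs an assumed 1 SD main effect and falls to 18% at 0.5 SD.

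Low power is also a fair objection. It argues for estimation, not for an analysis with no treatment term.

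**Conclusion.** The point holds in limited form. As written, the genotype analysis has no treatment contrast and does not answer the stated aim, and IAT/AAT are not clearly carried forward as predictors. Impulsivity and PIT are not affected, apart from the unstated timing of the impulsivity values.

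The direction of the error follows from the structure: a pooled correlation carries no information on the treatment difference. Its frequency rests on the assumed main effect, carrier share and variances, none of which the documents give.

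Severity is minor. The aim is exploratory, the trial is a pilot, and even the right analysis will give imprecise estimates.

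**What to change.** In Section V.4, Exploratory Aims:

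1. Add OPRM1, Fyn and STEP genotype and the pre-drug (ADP 1) IAT and AAT values to the sentence on predictors of treatment response. State that the impulsivity predictors, both tasks and self-report scales, also use pre-drug values.
2. Analyse each predictor by a predictor-by-treatment interaction in the Aim 1 mixed model, with treatment coded as three levels: NTX, NTX+MEM and NTX+NAC. Aim 1 now writes the factor as NTX against NTX+MEM/NAC, so this coding must be stated.
3. Report interaction estimates with 95% CIs, labelled exploratory and not adjusted for the number examined. Three genes, PIT and four tasks over two add-ons already make 8 × 2 = 16. If they were independent and all null, the chance that at least one interval excludes zero is 1 − 0.95¹⁶ = 56%. The self-report scales add more.
4. Keep the existing correlations as descriptions of alcohol response only.
5. State that OPRM1 results concern response to the add-on, because every medicated session includes naltrexone.

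The cost is plan wording and added model terms, with no new data. The intervals will be wide. The number genotyped may also fall below 30, because genetic consent is optional (Section V.3, Procedures; Section IX, Genetic Bloods).

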### ***Power Analysis***

This is a pilot trial and we will use the data to determine initial tolerability and effect size estimates for future trials. We will recruit a total of 30 completers in this trial, 10 in each group.

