***Naltrexone and alcohol drinking:***

Naltrexone's efficacy in reducing alcohol drinking is believed to be mediated through interactions between the endogenous opioid system and dopamine systems, specifically through antagonism of the mu-opioid receptors. The most commonly used dose of naltrexone of 50 mg/day has been shown to result in complete occupancy of the brain mu-opioid receptors (Weerts et al., 2008). Clinical trials indicate that treatment seeking drinkers who receive naltrexone at a dose of 50 mg/day in combination with a behavioral intervention have lower levels of relapse to drinking during the treatment period. However, it is important to note that not all the clinical trials conducted with naltrexone over the past decade have observed significant improvements in drinking treatment outcomes (e.g. Krystal et al., 2001), and two recent meta-analytical reports suggest that naltrexone has small to modest efficacy in preventing relapse to drinking (Bouza et al., 2004; Srisurapanont and Jarusuraisin, 2002). Moreover, while naltrexone is relatively well tolerated, the potential risk of hepatotoxicity at high doses requires caution in use in those with liver disease. A more recent multi-site trial which used a higher dose of naltrexone (100 mg/day) with medical management to enhance compliance found significant reductions of alcohol drinking with naltrexone, although again with a small effect size in the overall sample (Anton et al., 2006).

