In summary, the opioidergic system is an important modulator of alcohol effects and the opioid antagonist naltrexone has been shown to be effective at reducing alcohol drinking. Existing evidence also suggests that naltrexone may reduce alcohol drinking by attenuating craving for alcohol and that variants of the OPRM1 gene and family history of alcoholism may predict treatment response. However, the overall efficacy of naltrexone in reducing alcohol drinking is rather modest, with most clinical trials documenting a medium effect size. Interestingly, in our earlier project (HIC # 9912011476 ), while we observed significant naltrexone-induced reductions in drinking in FHP drinkers, these changes were not accompanied by consistent changes in alcohol craving or alcohol reward. All the above evidence suggests that there is room for improvement and a great need for medication approaches that have greater efficacy in reducing alcohol use.

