***Justification for choice of naltrexone dose:***

We will use naltrexone in a dose of 50 mg/day. This is the dose of naltrexone that is FDA approved for the treatment of alcohol dependence and has been most commonly used in most clinical trials (Anton et al., 2005; O'Malley et al., 1992; Volpicelli et al., 1992) and laboratory studies (Davidson et al., 1999; O'Malley et al., 2002; Anton et al., 2004). This dose also produces complete blockade of the mu-opioid receptors (Weerts et al., 2008). The 100 mg/day dose has also shown efficacy in many recent clinical trials (e.g., Anton et al., 2006), and our own preliminary evidence suggests that this dose may produce greater reduction in drinking in FHP drinkers than the 50 mg dose. However, in the proposed "proof of concept" trial we did not want to run the risk of missing the signal for a synergistic effect of memantine or NAC by combining it with a dose of naltrexone, which had a large effect of its own. Moreover, now that we are combining two medications we want to use a lower dose of naltrexone to minimize side effects from the combined pharmacotherapy.

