i) Psychophysiological Measures: These will include heart rate and blood pressure monitored using a Critikon Dinamap while skin temperature will be measured using Yellow Springs Instruments 4600 precision thermometer. The cuff of the Dinamap will be on the subject's dominant arm while the probe of will be attached to the middle finger of the subject's non-dominant arm. These data will be further used to examine the safety of using the medication combination during alcohol self-administration.

4. **Statistical Considerations:** Describe the statistical analyses that support the study design.

All outcomes will be summarized descriptively and assessed for normality prior to analysis using normal probability plots and Kolmogorov test statistics. Transformations or nonparametric analyses will be performed as necessary. In the mixed models described below, the correlation between repeated measures on an individual will be modeled using random effects and/or structured variance-covariance matrices. The best-fitting variance-covariance structure will be determined by information criterion. The mixed-effects approach is advantageous in that it is unaffected by randomly missing data and allows greater flexibility in modeling the correlation structure of repeated-measures data (Gueorguieva and Krystal, 2004). In the models below, we will test for order effects, although any such effects should be greatly minimized with the inclusion of the baseline session. All tests will be two-sided and considered statistically significant at alpha=.05. Significance levels for secondary comparisons will be adjusted for multiple tests using the Bonferroni correction, basing the adjustment on the number of conceptually related statistical tests within each hypothesis.

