**Aim 1:** Total number of drinks consumed during the self-administration period will be compared among treatment conditions using linear mixed models with treatment (NTX vs. NTX+MEM/NAC) included as a within-subjects factor. In these models, we will also consider baseline drinking, as assessed by using the 90 day TLFB obtained at intake, as a potential covariate. Non-significant covariates will be dropped for parsimony. A significant treatment effect, where total number of drinks is reduced during combination NTX+MEM/NAC treatment compared to NTX alone, will be supportive of our hypothesis. Secondary measures of alcohol-drinking typology such as average time to consume each drink and inter-sip interval will be analyzed using similar models as described above, whereas time to first drink during the ad-lib drinking period will be analyzed using survival models with subject-specific frailties to account for correlation of the repeated survival outcomes within individuals.

**Aim 2:** Scores on the Yale Craving Scale will be the primary outcome in this aim and will represent the dependent variable in a linear mixed model evaluating combination treatment effects of NTX and MEM/NAC on alcohol craving. The model will include treatment (NTX vs. NTX+MEM/NAC) and time (see study time points, Table 1) as within-subjects explanatory factors, and random subjects effects. The interaction between treatment and time will be modeled and interpreted using graphical displays and appropriate post-hoc tests. We anticipate a significant treatment by time interaction explained by greater reductions in craving over time among combination NTX+MEM/NAC compared to NTX alone. A secondary measure of craving, the Alcohol Urge Questionnaire, will be analyzed using the same model described above. We will also explore the influence NTX vs. NTX+MEM/NAC on YCS alcohol craving in response to the alcohol cue exposure just prior to the start of the priming drink period using a similar model.

**Aim 3:** Alcohol-induced stimulation, measured by the Biphasic Alcohol Effects Scale (BAES), will be analyzed using the same model described for alcohol craving in Aim 2. A significant treatment by time interaction, explained by reduced alcohol stimulation to due to combination

NTX+MEM/NAC treatment, compared to NTX alone, will be supportive of our hypothesis. A secondary analysis will conduct similar comparisons on the sedation scores obtained using the BAES.

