**5. Potential Benefits:** Identify any benefits that may be reasonably expected to result from the research, either to the subject(s) or to society at large. (Payment of subjects is not considered a benefit in this context of the risk benefit assessment.)

This study will not directly benefit the participants. The results of this laboratory-based drinking paradigm will provide help advance knowledge in the area of development of pharmacotherapies for alcohol drinking. An additional benefit to subjects is that they will be offered feedback about

their drinking and active referral to treatment for their alcohol problems should they so desire. Most alcohol abusers have impairments in their psychosocial functioning as a result of their drinking and can benefit from treatment. The proposed study may be a conduit for some to receive treatment and for others to reduce their drinking on their own. Although the direct benefit is not great for subjects, given the potential benefit to developing effective treatments for alcoholism, the risk-benefit ratio appears favorable.

Furthermore, the results of this laboratory-based drinking paradigm will provide an important initial signal regarding the potential efficacy of the combination of naltrexone and memantine or Nacetylcysteine in reducing alcohol drinking. There is a great need for the development of new agents and combination of agents to treat alcohol dependence, particularly in subpopulations of drinkers. This laboratory paradigm will also provide information regarding the mechanism of action of these agents and thus significantly contribute to the literature.

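### Is a pilot of 30 completers too small for the significance tests by which its primary aims are read?

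*Combined protocol and SAP*

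**What the plan says.** The Power Analysis paragraph in Section V.4 calls the study a pilot and says "we will use the data to determine initial tolerability and effect size estimates for future trials". It then fixes the number: "We will recruit a total of 30 completers in this trial, 10 in each group". It gives no effect size, SD, correlation, power or interval width.

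The opening of Section V.4 states: "All tests will be two-sided and considered statistically significant at alpha=.05". For Aim 1 the result counted as supporting the hypothesis is "A significant treatment effect, where total number of drinks is reduced during combination NTX+MEM/NAC treatment compared to NTX alone". Aim 3 has a parallel sentence for a treatment-by-time interaction. For Aim 2 the plan only anticipates a significant interaction. None of the three aims says what a non-significant result would mean.

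The design (Section V.3) is a crossover with three regimens and two medication periods, so each person receives two of the three. Section II.3 gives 86 as the enrolment target and as the number expected to complete at least part of the interventions.

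The Background says that "the overall efficacy of naltrexone in reducing alcohol drinking is rather modest, with most clinical trials documenting a medium effect size". It also cites meta-analyses in which "naltrexone has small to modest efficacy in preventing relapse to drinking". Section IX.5 says the results "will provide an important initial signal regarding the potential efficacy of the combination of naltrexone and memantine", or with N-acetylcysteine.

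**The concern.** The sample size is justified by estimation, while the primary aims are read through p-values. If the add-on effect is no larger than the small-to-medium effect the Background gives for naltrexone itself, a test on 30 completers will often fail to reach .05 even though the effect is real. A reader who took non-significance as evidence against the combination would lose the early signal that Section IX.5 promises.

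The dose rationale in Section V.3 seems to sharpen this, since it says "we did not want to run the risk of missing the signal for a synergistic effect of memantine or NAC". There is also a possible knock-on effect. If only significant results led to a further trial, the estimates carried forward would be too large on average.

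**Working it through.** The plan has no power figure to reproduce, so the check asks what 30 completers can deliver.

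**Inputs from the documents**
- 30 completers, 10 per group (Power Analysis)
- two-sided alpha .05 (Section V.4)
- three regimens, two periods per person (Section V.3)

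**Assumptions, not in the documents**
- groups are the three possible pairs of regimens, 10 people each, with order balanced
- effect 0.5 between-person SD, set against the medium effect the Background gives for naltrexone
- between-session correlation r from 0.3 to 0.8

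**Information per combination.** Let s be the SD of the within-person difference in drinks.
- The 10 people who take both naltrexone alone and a given combination give variance s²/10.
- The other two pairs give an indirect comparison with variance s²/10 + s²/10 = s²/5.
- The precisions add: 10 + 5 = 15 pair equivalents.
- Two crossovers of 15 people each also give 15.
- Error degrees of freedom: 30 differences less a period term and two treatment terms = 27.

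**Half-width of the 95% interval.** t(0.975, 27)/√15 = 2.052/3.873 = 0.53 s.

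**Power at a given effect in units of s** (noncentral t, noncentrality = effect × √15):

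| Effect (in s) | Power |
|---|---|
| 0.2 | 12% |
| 0.3 | 20% |
| 0.5 | 46% |
| 0.8 | 85% |

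Power reaches 80% at about 0.75 s.

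**Conversion to between-person SD.** An effect of d between-person SDs equals d/√(2(1 − r)) in units of s. For d = 0.5:

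| r | Effect in s | Power | Miss rate |
|---|---|---|---|
| 0.3 | 0.423 | 35% | 65% |
| 0.5 | 0.500 | 46% | 54% |
| 0.7 | 0.645 | 67% | 33% |
| 0.8 | 0.791 | 84% | 16% |

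The two SD scales agree only at r = 0.5.

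**Pooled reading.** Aim 1 writes the treatment factor as naltrexone against naltrexone plus either agent, which can be read as two levels. At r = 0.5 the pooled contrast has 20 pair equivalents with three pairs, or 30 with two crossovers, on 28 degrees of freedom. Power is 58% and 75%, so the miss rates are 42% and 25%.

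**The 86.** If about 84 people completed (28 per pair), the miss rate per combination at r = 0.5 would be 11%. The Power Analysis plans on 30, and 86 people completing part or all of the interventions is compatible with 30 completing everything.

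**Does the text produce the feared harm?**
- *Verdict on a null result.* The support sentences for Aims 1 and 3 run one way: significance supports the hypothesis. The plan contains no rule for declaring a hypothesis unsupported and no go/no-go rule.
- *The dose sentence.* It continues by naming the risk as pairing the add-on with a naltrexone dose that has a large effect of its own. It explains 50 mg rather than 100 mg and says nothing about sample size.
- *Inflated estimates for later trials.* This needs a further trial to be triggered by significance. The Power Analysis uses the estimates without that condition.
- *Availability of estimates.* A linear mixed model with a treatment factor yields the treatment difference and its standard error, so the product promised in the Power Analysis comes from the analysis already specified.

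**The case for a change.** The best case for a change is textual and needs no assumed effect. A section headed Power Analysis gives neither power nor precision, and the aims state their success criterion as significance without mentioning an interval. A wording change would cost nothing in participants: report each combination's difference with its 95% interval, state the half-width, and say that non-significance in a pilot is not evidence against the combination. The 54% is not a worst case either. Using only the 10 direct pairs, the miss rate is 71% at a correlation of 0.5, and splitting alpha across the two combinations gives 65%.

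Much of this stands as description. The two parts of Section V.4 do point in different directions, and power for a medium effect is low under most of the assumptions tried. The intervals would make a better report, and a line defining group and relating the 30 to the 86 would help readers. But these are details that an analyst reporting a pilot would supply from the same models. Relabelling the pre-specified tests as descriptive has a price, because it gives up a yes/no reading of each hypothesis, and statisticians would differ on that trade. Raising the completer target would be a request for a larger study, and nothing the pilot promises requires it.

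**Conclusion.** The arithmetic behind the worry is right, but it shows low power in a declared pilot and no defect in the plan. For a 0.5 between-person SD effect, each combination would miss significance about 65% to 16% of the time for correlations of 0.3 to 0.8. At a correlation of 0.5 a pooled contrast would miss 42% or 25% of the time, depending on how people are allocated to pairs. These figures rest on an assumed effect, an assumed correlation, balanced pairs and least squares on completers' differences. The planned mixed models could do somewhat better if partial data are used.

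The plan states no power that these figures contradict. A significant result keeps its meaning at this size, no adverse conclusion is attached to a non-significant one, and the effect estimates come out of the specified models. What remains is reporting detail and a trade-off between estimation and testing that the investigators were entitled to settle as they did.
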